#### 5.3 Details of processing/analysis

The PET/CT scans will be interpreted by ABNM certified Nuclear Medicine physicians, while the PET/MRI scans will be reviewed by ABNM certified Nuclear Medicine physicians and ABR certified Radiologists. All these investigators have significant clinical experience and will be blinded to the participants' medical history and the results of other imaging modalities. Consensus read will be obtained for each scan. Each lesion will be tabulated and a comparison of lesion detection by each scanner will be conducted.

#### 6. STUDY PROCEDURES

#### 6.1 Criteria for Removal from Study

The Protocol Director may withdraw subjects from the study for one or more of the following reasons: failure to follow the instructions of the Protocol Director and/or study staff; determination that continuing the participation could be harmful to the subject; the study is cancelled or other administrative reasons.

#### 6.2 Alternatives

The alternative is to not participate in the study.

#### 7. STUDY CALENDAR

	Pre- Study	Week 1	12 Months
Informed consent	х		
Demographics	Х		
Medical history	Х		
 F FDG or  Ga DOTA TATE PET/CT and PET/MRI done on the same day		x	
Data analysis			Х

#### 8. ADVERSE EVENTS AND REPORTING PROCEDURES

#### 8.1 Potential Adverse Events

The administration of the radioactive substance will feel like a slight pinprick if given by intravenous injection. Patients who are claustrophobic may feel some anxiety while positioned in the scanner. Also, some patients find it uncomfortable to hold one position for more than a few minutes. The subjects will not feel anything related to the radioactivity of the substance in their body. Because the radioactivity is very short-lived, the radiation exposure is low. The substance amount is so small that it does not affect the normal processes of the body.

There will be a single injection of F FDG or Ga DOTA TATE followed by 1 PET/CT scan and 1 PET/MR scan. There will be no additional radiation to the patient. This is because only one injection of F FDG or Ga DOTA TATE will be given and the MRI uses nonionizing radiation.

Magnetic fields do not cause harmful effects at the levels used in the MRI machine. However, the MR scanner uses a very strong magnet that will attract some metals and affect some electronic devices. All such metallic objects must be removed (if possible) before entering the magnet room. In some cases, having those devices means the patient should not have an MRI scan performed. In addition, watches and credit cards should also be removed as these could be damaged. There is a possibility that the patient will experience a localized twitching sensation due to the magnetic field changes during the scan. This is expected and should not be painful. If the patient had a previous reaction to gadoliniumbased contrast agents, a history of severe allergies, or a history of kidney disease, he/she should notify the operator/investigator.

#### 8.2 Adverse Event Reporting

We do not anticipate hazardous situations for the subjects as a result of this protocol. However, procedures will be in place for verification of correct radiopharmaceutical dose and route of administration (i.e., each dose will be double checked for dosimetry and quality by a researcher and technologist). The study Principal Investigator (PI) or his designee will report unanticipated AEs related to the Stanford CCTO Safety Coordinator within 10 working days of becoming aware of the event (5 days if the event is life-threatening or resulted in death) using the Adverse Events Communication Form. If the principal investigator determines the unanticipated adverse device effect presents an unreasonable risk to subjects, the study will be terminated as soon as possible, but no later than 5 working days after first receiving notification of the effect.

#### 9. REGULATORY CONSIDERATIONS

#### 9.1 Institutional Review of Protocol

The protocol, the proposed informed consent and all forms of participant information related to the study (e.g. advertisements used to recruit participants) will be reviewed and approved by the Stanford IRB. Any changes made to the protocol will be submitted as a modification and will be approved by the IRB prior to implementation. The Protocol Director will disseminate the protocol amendment information to all participating investigators.

#### 9.2 Data Management Plan

The CRFs will be stored in a locked office in the Nuclear Medicine clinic. Records will be kept using OnCore.

During the clinical investigation, the Protocol Director will evaluate the progress of the trial, including periodic assessments of data quality and timeliness, participant recruitment, accrual and retention, participant risk versus benefit, performance of trial sites, and other factors that can affect study outcome. Monitoring of the trial will occur every 8 weeks and a record of monitoring activities will be maintained by the study team.

The Stanford Cancer Institute Data and Safety Monitoring Committee (DSMC) will audit study related activities to determine whether the study has been conducted in accordance with the protocol, local standard operating procedures, FDA regulations, and Good Clinical Practice (GCP). This may include review of regulatory binders, case report forms, eligibility checklists, and source documents. In addition, the DSMC will regularly review serious adverse events and protocol deviations associated with the research to ensure the protection of human subjects. Results of DSMC audits will be communicated to the IRB and the appropriate regulatory authorities at the time of continuing review, or in an expedited fashion, as needed.

#### 10. MEASUREMENTS

#### **10.1 Primary outcome measure**

We will evaluate the maximum standardized uptake value (SUVmax) of F FDG or Ga DOTA TATE in the lesions detected with both scanners. There are now several papers based on other vendors' scanners (no GE PET/MRI scanner built yet). The authors showed that in oncologic patients examined with PET/CT and PET/MRI, the SUVmax values generally correlate well in normal organ tissues. SUVmax derived from PET/MRI can be used reliably in clinical routine. Differences observed between MRI and CT derived SUV values may be attributed to the time-delay between the PET/CT and PET/MRI scans or biologic clearance of radiotracer (*10, 11*).

#### **10.2 Measurement Methods**

Regions of interest will be placed around the lesions using the AW software (GE Healthcare) and the  $SUV_{max}$  values from the images acquired with both scanners will be recorded.

#### **10.3 Measurement Time Points**

SUVmax values of the lesions will be measured after the scan completion.

#### 10.4 Response Review

The  $SUV_{max}$  values will be analyzed by Nuclear Medicine and Radiology physicians blinded to the diagnosis and results of the other scan, in a randomized order to avoid bias. Two physicians will review all scans independently. Both scans of a given patients will be analyzed by one physician, then separately by the second physician.

#### **11. STATISTICAL CONSIDERATIONS**

#### 11.1. Statistical Design

Single arm prospective study of paired imaging studies.

#### 11.2. Randomization

This study is to compare the images from two different scanners: PET/CT and PET/MR and patients are scanned with both scanners. No randomization will be done.

#### 11.3. Interim analyses

No interim analyses are planned.

#### 11.4. Descriptive Statistics and Exploratory Data Analysis

(see below)

#### 11.5. **Primary Analysis**

#### 11.1.1. Analysis Population

Analysis population: all lesions identified by either modality (per-lesion analysis).

#### 11.1.2. Analysis Plan

Normal quantile plots of  $SUV_{max}$  for each scanner will be prepared to assess to what extent the distribution can be approximated by the normal distribution, and to suggest a suitable transformation if not. The distribution of  $SUV_{max}$  for each scanner will be summarized with means, standard deviations, range, median and upper and lower quartiles. The distribution of the difference ( $SUV_{max}$ \_PET/CT –  $SUV_{max}$ \_PET/MRI) (difference of transformed values if applicable) will likewise be summarized. Cumulative distribution (waterfall plots) may be prepared to assist in the evaluation of the results. Patient clinical and demographic characteristics will be summarized using relevant summaries (proportions for categorical variables, means and standard deviations for continuous variables.

The mean difference plus or minus twice the standard deviation of the difference will be calculated as a measure of absolute accuracy. The relative accuracy will be calculated by dividing the preceding interval by the arithmetic average of the mean  $SUV_{max}$  of the two scanners. The interpretation of these intervals is that we can expect that approximately 95% of future differences to lie in these intervals. A paired t-test will be used to aid in the interpretation of the results. Sensitivity analyses may be conducted using linear mixed effects models to account for possible clustering of lesions within patients.

The difference of  $SUV_{max}$  measures will be correlated with patient and lesion characteristics and with time after injection using the appropriate method (Pearson correlation for continuous variables such as age and time from injection, two-sample t-tests for binary attributes (sex) and analysis of variance for categorical variables).

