#### 11.6. Sample Size

Data from Kershah (*10*) shows coefficients of variation between SUV measurements between PET/CT and PET/MRI ranging from 0.21 to 0.51, about 0.33 for CT attenuation correction and 0.38 for MR attenuation correction. We present calculations assuming a CV of 0.38 for both modalities and a Pearson correlation of 0.5 (moderate scenario) and 0.9 (optimistic scenario). Assuming a Pearson correlation of 0.5 on the log scale, 200 subjects provide 80% power to detect a relative difference of 8% between the SUVmax values using the two modalities. With an optimistic assumption of a Pearson correlation of 0.9, 200 patients provide 80% power to detect a relative difference of 3.4%. These differences do not seem minute, they will be a bit larger with only 100 subjects: assuming a Pearson correlation of 0.5 on the log scale, 100 subjects provides 80% power to detect a relative difference of 11% between the SUVmax values using the two modalities. With an optimistic assumption of a Pearson correlation of 0.5 on the log scale, 100 subjects provides 80% power to detect a relative difference of 11% between the SUVmax values using the two modalities. With an optimistic assumption of a Pearson correlation of 0.9, 200 patients provide 80% power to detect a relative difference of 5%.

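### The measurement scale is chosen from each scanner's SUVmax distribution, not from how the paired differences behave across uptake, so the ±2 SD limits can cover unevenly at low and high uptake.

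*Combined protocol and SAP*

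**What the plan says.** All of this is in the combined protocol and SAP. Section 11.1.2 (Analysis Plan, under Primary Analysis) starts from the SUVmax values of the two modalities taken separately. It says that quantile plots, one set per modality, "for each scanner will be prepared to assess to what extent the distribution can be approximated by the normal distribution". Where that check fails, the same plots have a further purpose: "and to suggest a suitable transformation if not". The paired difference comes second: the "difference of transformed values if applicable) will likewise be summarized". An optional display follows: "Cumulative distribution (waterfall plots) may be prepared to assist in the evaluation of the results". It is not linked to the choice of scale.

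The agreement measure is then fixed: "The mean difference plus or minus twice the standard deviation of the difference will be calculated as a measure of absolute accuracy". A relative version is obtained by "dividing the preceding interval by the arithmetic average of the mean" SUVmax of the two scanners. The plan adds: "The interpretation of these intervals is that we can expect that approximately 95% of future differences to lie in these intervals". A paired t-test is used as an aid to interpretation. The difference is also correlated with patient and lesion characteristics and with time from injection.

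Section 11.6 (Sample Size) works with a CV of 0.38 and relative differences, for example "Assuming a Pearson correlation of 0.5 on the log scale". Section 11.1.2 does not commit to that scale.

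**The concern.** Limits of the form mean ± 2 SD describe agreement equally well at all uptake levels only if the differences are roughly normal and their spread is the same at low and high SUVmax. A near-normal SUVmax distribution on each scanner does not secure this, and a skewed one does not rule it out. The distribution used to choose the scale is therefore not the one on which the limits depend.

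Nothing else in the plan fills the gap. There is no quantile plot of the differences and no plot of difference against mean uptake. The planned correlations use the signed difference, so they can show a shift in bias but not a change in spread. The relative limits divide one interval by one overall mean; this rescales the interval by a constant and does not adapt it to uptake.

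What is at stake is how the main agreement result is read. If error grows with uptake and the raw scale is kept, agreement is overstated for high-uptake lesions, where disagreement in SUV units is largest, and understated for low-uptake lesions. Overall coverage would not reveal this.

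**Working it through.** **1. The plan's own figures and their scale.** Inputs from 11.6: CV 0.38, correlation 0.5 or 0.9, power 80%. Alpha is not stated; I assume 0.05 two-sided. SD of the log difference = 0.38 × √(2(1 − r)). Detectable ratio = exp((1.960 + 0.842) × SD / √N) − 1.
- r = 0.5, N = 100: SD 0.38, exp(2.802 × 0.038) − 1 = 11.2% (stated 11%).
- r = 0.5, N = 200: 7.8% (stated 8%).
- r = 0.9, N = 200: SD 0.170, 3.4% (stated 3.4%).

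The sample size therefore does rest on a log-scale model. Constant spread on the log scale means that raw differences grow with uptake.

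**2. Why raw limits then cover unevenly.** Suppose there is no bias and the SD of the raw difference at uptake m is c·m. The overall SD is c·m̄·√(1 + CV²), with m̄ the mean and CV the coefficient of variation of uptake. Coverage at uptake m is 2Φ(2√(1 + CV²)·m̄/m) − 1. The constant c cancels, so the unevenness comes from proportionality, not from the size of the error. With an assumed CV of 0.36, 2√(1 + 0.36²) = 2.126:
- m = 0.5 m̄: z = 4.25, coverage practically 100%.
- m = m̄: z = 2.13, about 97%.
- m = 1.5 m̄: z = 1.42, about 84%.

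**3. Near-normal uptake, proportional error.** Simulation of 1,000,000 pairs per case. A Shapiro-Wilk test on samples of 100 stands in for reading the quantile plots. The true-value and error CVs are assumptions.

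| | True CV 0.36, error 0.12 | True CV 0.33, error 0.10 |
|---|---|---|
| Scanner CV; correlation | 0.375; 0.885 | 0.343; 0.906 |
| Raw-limit coverage, overall | 94.5% | 94.6% |
| Lowest third | 99.6% | 99.6% |
| Highest third | 87.7% | 88.0% |
| Top tenth | 81.9% | 82.3% |
| Either scanner flagged as non-normal | 22% | 15% |
| Rank test of absolute difference on mean detects the problem | 96% | 94% |

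Across runs with similar inputs (error 8-12%), the either-scanner flag rate was 11-24%, highest-third coverage 87-88% and top-tenth coverage 79-83%.

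**4. The reverse error.** With skewed uptake (log-normal, log SD 0.6; SUVmax skewness 2.2) and constant additive error, raw limits cover about 95.4% at every level, so no transformation is needed. The skewed per-scanner plots would nevertheless prompt one. Limits on the log differences then cover 69% in the lowest tenth, 87% in the lowest third and 100% in the highest third.

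**5. A case the plan handles.** With log-normal SUVmax at CV 0.38 on both scanners, the per-scanner check flags a transformation in about 99% of samples of 100 (72% at CV 0.21). Limits on the log differences then cover about 95.5% at every level.

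**6. Would testing the differences for normality do instead?** No. It flags only about 32-45% of samples of 100 across these cases, including 46% in one log-normal run at CV 0.38. Spread against the mean is the informative check.

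**The case against.** Several stronger readings are tempting, and the documents do not support them.

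- **That the 95% statement fails.** It is a statement about future differences overall. Overall coverage was 94.5-95.1% in the log-normal cases at CV 0.21 and 0.38 and in the near-normal cases. The plan does not promise 95% at each uptake level.
- **That the paired t-test is invalid.** It does not need constant spread across uptake. Its simulated size was 3.7-6.1% with 100 to 500 independent lesions, and the plan uses it only as an aid.
- **That top-tenth coverage would be 76-77%.** That is the raw-scale figure for log-normal SUVmax at CV 0.38. There the plan's own rule would almost always lead away from the raw scale, so the figure should not arise.
- **That 11.1.2 contradicts 11.6.** Under the assumptions of 11.6 the rule would prompt a transformation. The scale is left open; the sections are not in conflict.

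It can also be said that near-normal SUVmax is an assumption. The plan takes all lesions, any cancer and two tracers, and nothing in it points to a normal shape. The unit is the lesion, so n may exceed 100: in a similar scenario the either-scanner flag rate rises to about 41% with 300 independent lesions and 59% with 500. Quantile plots read by eye also have no fixed threshold.

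These points stand and limit how likely the raw-scale error is. They do not remove the gap. Skewed SUVmax makes the reverse error possible, and in neither direction would a planned display show it.

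**Conclusion.** The point holds as a matter of method: the scale is chosen from the wrong distribution, and the spread of the differences across uptake is never examined. The consequence is uptake-dependent coverage. Under proportional error with near-normal uptake, raw limits cover about 99.5% in the lowest third, 87-88% in the highest third and 79-83% in the top tenth. Under additive error with skewed uptake, an unneeded log transform undercovers at low uptake.

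This is a risk, not a certainty. The error models are assumed because the documents give no lesion-level SUVmax data, lesions are treated as independent, and a formal test stands in for visual plots. The result is also weaker at low correlation: with an assumed error CV of 0.27 (correlation 0.48), the per-scanner check flags 70% of samples, the rank test detects 63%, and highest-third raw coverage is 90%. The change is still worth making because it costs almost nothing.

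**What to change.** Amend section 11.1.2 before the data are analysed:

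1. Make limits of agreement on the log-ratio scale the default: geometric mean ratio and ratio limits, each with a confidence interval. This matches 11.6.
2. Judge the scale from the paired data by plotting the difference and its spread against the mean of the two scanners, on both scales. Add a quantile plot of the differences as a supplement, not as the deciding check.
3. Report raw-scale limits as secondary, and state that they are preferred if the difference-versus-mean plot shows constant raw spread.
4. Keep the per-scanner quantile plots as description only.

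The cost is wording and one extra plot, with no new data or visits. Results would be read as ratios and not in SUV units. Log limits would be the poorer choice if error is additive, which is why item 3 is needed.

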#### 1. OBJECTIVES

#### 1.1 Primary Objective

 To evaluate if PET/CT and PET/MRI scanners provide equivalent results for evaluation of cancer patients

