#### 2.4 Rationale

The Division of Nuclear Medicine and Molecular Imaging at Stanford has two of the most modern PET/CT scanners from GE Healthcare, the Discovery 600 PET/CT and Discover 690 PET/CT scanners. There will be a novel GE PET/MRI scanner installed at the Lucas Imaging Center. This will be the first of this kind to be produced by GE Healthcare. Therefore it is important to determine if PET/CT and PET/MRI scanners provide equivalent results for evaluation of cancer patients.

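### The only objective is equivalence of the two scanners, but the primary analysis sets no acceptance limit for the mean difference or the limits of agreement, and its t-test ignores clustering of lesions

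*Combined protocol and SAP*

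**What the plan says.** Section 1.1 gives one objective: "To evaluate if PET/CT and PET/MRI scanners provide equivalent results for evaluation of cancer patients". Section 2.4 repeats it: "it is important to determine if PET/CT and PET/MRI scanners provide equivalent results for evaluation of cancer patients". The contents list has an entry for secondary objectives, but the body contains none.

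The primary analysis is per lesion, in "all lesions identified by either modality (per-lesion analysis"). Section 11.1.2 plans normal quantile plots to check the distribution "and to suggest a suitable transformation if not", then summaries of the paired difference. The main agreement statistic follows: "The mean difference plus or minus twice the standard deviation of the difference will be calculated as a measure of absolute accuracy". A relative version divides that interval by the average of the two scanner means. The only stated interpretation is: "The interpretation of these intervals is that we can expect that approximately 95% of future differences to lie in these intervals". Two sentences complete the inferential part: "A paired t-test will be used to aid in the interpretation of the results" and "Sensitivity analyses may be conducted using linear mixed effects models to account for possible clustering of lesions within patients".

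Section 11.6 gives differences detectable with 80% power, assuming a CV of 0.38 and correlations of 0.5 and 0.9. Its only comment on size is a passing remark that these differences are not tiny. Section 11.7 expects 100 patients.

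**The concern.** An agreement interval answers a question about equivalence only when it is set against a limit. The stated interpretation, that about 95% of future differences fall inside, applies equally to a narrow interval and a very wide one. The t-test addresses whether the mean difference is zero, and section 11.6 addresses the chance of detecting a non-zero difference. Neither supplies the missing limit. Section 11.8, on criteria for future studies, sets no success criterion either.

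Followed as written, the plan produces relevant numbers but no prespecified way to turn them into an answer to its one question. Two teams could report the same result in opposite ways.

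Two features would also make a limit hard to apply. The analysis scale is to be chosen from the data. The lesion set differs between sections: 10.1 refers to lesions detected on both scanners, 11.1.1 to lesions identified on either.

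**Working it through.** **Inputs.** From section 11.6: CV 0.38 for both scanners, correlation ρ = 0.5 or 0.9, 80% power. From section 11.7: n = 100. The significance level is not stated; two-sided 0.05 is assumed. The reference list shows that the CVs come from a study of normal structures, so lesions may differ. Unless stated otherwise, each patient contributes one independent pair.

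**Step 1: reproduce section 11.6.** SD of the log difference = s√(2(1−ρ)). Detectable log difference d = (1.960 + 0.842) × SD/√n. Relative difference = exp(d) − 1. With s = 0.38:

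| n | ρ | SD | Recomputed | Plan |
|---|---|---|---|---|
| 200 | 0.5 | 0.380 | 7.8% | 8% |
| 200 | 0.9 | 0.170 | 3.4% | 3.4% |
| 100 | 0.5 | 0.380 | 11.2% | 11% |
| 100 | 0.9 | 0.170 | 4.9% | 5% (printed with 200 patients) |

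The plan's figures are therefore detectable differences for a test of zero difference. They are not equivalence limits. The 200 in the last row looks like a slip for 100, which is a separate matter.

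**Step 2: the plan's own relative interval.** With mean difference 0 and ρ read on the raw scale, the half-width is 2 × CV × √(2(1−ρ)):
- ρ = 0.5: 2 × 0.38 × 1 = 0.76, or ±76%.
- ρ = 0.9: 2 × 0.38 × 0.447 = 0.34, or ±34%.

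**Step 3: mean and limits compared, n = 100, true ratio 1.** Here s = √ln(1 + 0.38²) = 0.3673, so SD = 0.3673 (ρ 0.5) or 0.1642 (ρ 0.9). The 90% CI of the mean ratio is exp(±1.660 × SD/10). The limits of agreement are exp(±2 × SD).

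| ρ | 90% CI of mean ratio | Limits of agreement |
|---|---|---|
| 0.5 | 0.94 to 1.06 | 0.48 to 2.08 |
| 0.9 | 0.97 to 1.03 | 0.72 to 1.39 |

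The mean can be pinned close to 1 while single lesions differ up to about two-fold. The limits are estimates too: the standard error of a log limit is SD × √(1/100 + 4/(2 × 99)) = 0.174 × SD. At ρ = 0.5 the upper limit of 2.08 has an approximate 90% CI of 1.87 to 2.32.

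**Step 4: can the t-test stand in?** Noncentral t, 99 df, true difference 10%. At ρ = 0.5 the test is non-significant 27% of the time (s = 0.3673) or 30% (s = 0.38). At ρ = 0.9 the figure is under 1%.

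**Step 5: clustering (illustration).** Lesions per patient k and within-patient correlation of the differences c are assumptions, because the documents give neither. Design effect D = 1 + (k−1)c. A nominal 90% CI that ignores clustering covers 2Φ(1.645/√D) − 1.

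| k | c | D | Coverage |
|---|---|---|---|
| 2 | 0.3 | 1.3 | 85% |
| 2 | 0.6 | 1.6 | 81% |
| 5 | 0.3 | 2.2 | 73% |
| 5 | 0.6 | 3.4 | 63% |

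**Step 6: equivalence power (illustration).** The margins are assumptions. With margin 1/m to m and true ratio θ, power = Φ((ln m − ln θ)/se − t) − Φ((−ln m − ln θ)/se + t), where se = SD/10 and t = 1.660. At ρ = 0.5, with the range covering s = 0.38 to 0.3673:
- m = 1.11: 72–76% at θ = 1; 41–44% at θ = 1.05.
- m = 1.15: 96–97% at θ = 1; 77–79% at θ = 1.05.

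**The case against.** The strongest defence is that this is an estimation plan. It is a single-arm paired study of a new scanner, it leads with limits of agreement, it says what they mean, and it gives the t-test a supporting role. Readers can set the reported limits against their own tolerance, and the choice of tolerance is clinical. Much of this stands: the method is sound and the data would be useful. But the stated question is equivalence, and the plan does not say what would count as equivalent.

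Some stronger readings should be resisted.
- A reader might infer that the plan treats a non-significant t-test as proof of equivalence. It does not say so. Step 4 shows only that the test cannot fill the gap.
- A reader might cross the ends of the cited CV range (0.21 and 0.51) with the two correlations to get a much wider spread of limits. Section 11.6 applies its correlations only to a CV of 0.38, so ±34% and ±76% are the figures its assumptions support.
- A reader might conclude that 100 patients are too few. Without a margin that cannot be said: Step 6 runs from 41% to 97% on assumed margins.
- The fixed order, PET/CT then PET/MRI, is a separate caveat. It is partly addressed by the planned correlation of the difference with time after injection.

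**Conclusion.** The concern holds in this form: the sole objective is equivalence, and no section gives an acceptance limit or decision rule for the mean or for the limits of agreement. The absence is plain from the text and rests on no assumption. Its consequence, at the plan's CV of 0.38, is that relative limits of about ±76% or ±34% are both compatible with the planning assumptions and neither is classed as acceptable or not.

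The clustering weakness is also real, because the primary t-test is per lesion and the mixed model is optional. Its size is unknown from the documents; the 85% to 63% coverage figures rest on assumed lesion counts and correlations. The point should be fixed before analysis. It does not undermine the data collected.

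**What to change.** Before analysis, revise sections 10.1, 11.1.1, 11.1.2 and 11.6:

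1. Fix the log (ratio) scale already used in 11.6. State investigator-chosen limits for the mean SUVmax ratio and for the limits of agreement.
2. Conclude equivalence of the mean only if the 90% CI of the ratio lies wholly inside the margin. Take that CI from a linear mixed model with a patient random effect, made primary rather than optional. Keep the t-test as descriptive.
3. Compute the limits of agreement from the total (between- plus within-patient) variance. Judge them by their confidence bounds rather than point estimates, and report them separately, so that a close mean is not read as interchangeability for single lesions.
4. Reconcile 10.1 with 11.1.1: use every lesion with an SUVmax measured on both scanners, including one first identified on a single scanner if the same site can be measured on the other. Report lesions that cannot be measured on both under the detection comparison in section 5.3.
5. Restate 11.6 as equivalence power at n = 100 for the chosen margin, over a range of true ratios, correlations, lesions per patient and within-patient correlations.

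If no limits are set, reword the objective and conclusion as estimating agreement rather than showing equivalence.

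The cost is SAP wording, two prespecified limits and modest extra analysis, with no new scans or readers. The downsides are that stated power may look poor for a tight margin (41–44% in the 11% illustration at a true ratio of 1.05) and that the trial can formally fail to show equivalence.

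### The primary agreement limits have no confidence interval, and the planned paired t-test treats lesions of one patient as independent

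*Combined protocol and SAP*

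**What the plan says.** Section 11.1.1 sets the analysis population as "all lesions identified by either modality (per-lesion analysis"). It states no cap on lesions per patient, no weighting and no averaging within patient.

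Section 11.1.2 then gives the agreement measure: "The mean difference plus or minus twice the standard deviation of the difference will be calculated as a measure of absolute accuracy". A relative version divides the interval by the average of the two scanner means. The stated reading is that one can expect "approximately 95% of future differences to lie in these intervals".

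Two further sentences concern inference. "A paired t-test will be used to aid in the interpretation of the results", with no mention of patients as clusters. And "Sensitivity analyses may be conducted using linear mixed effects models to account for possible clustering of lesions within patients"; this is discretionary and does not say that the model would re-estimate the limits.

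Section 11.6 counts subjects, not lesions, and addresses power to detect a mean difference. It says nothing about how precisely the limits will be known.

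**The concern.** Section 1.1 asks whether the two scanners give equivalent results. No equivalence margin is stated, so the limits are the plan's main description of agreement. They are estimates, and a reader who sees only two numbers cannot tell a well-estimated limit from one that landed close to zero by chance.

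The second issue is the unit. Lesions in one patient share the injection, the delay between scans and the attenuation-correction conditions, so their PET/CT minus PET/MRI differences may well be correlated. A paired t-test over lesions then uses a standard error that is too small and can declare a systematic scanner difference far more often than its nominal 5%. A confidence interval added later at lesion level would have the same fault.

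**Working it through.** **Inputs from the documents.** CV 0.38 for both modalities, correlation 0.5 or 0.9 (Section 11.6); 100 patients expected (Section 11.7). Alpha is not stated; 0.05 two-sided is assumed.

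**1. Reproducing the plan's own figures.** On the log scale, taking 0.38 as the log SD, SD_d = 0.38 × √(2(1 − r)). This is 0.380 at r = 0.5 and 0.170 at r = 0.9. The detectable difference is exp[(1.960 + 0.842) × SD_d/√n] − 1:
- n = 200, r = 0.5: 7.8% (plan: 8%)
- n = 200, r = 0.9: 3.4% (plan: 3.4%)
- n = 100, r = 0.5: 11.2% (plan: 11%)
- n = 100, r = 0.9: 4.9% (the plan's 5% matches this n)

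The inputs are therefore read as the plan uses them, with one difference per patient.

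**2. Is the 95% reading right?** For n independent normal differences, the expected content of mean ± 2 SD is P(|t with n − 1 df| < 2/√(1 + 1/n)). At n = 100 this is 95.1%. In simulations with clustered lesions, average content stayed at 94.4–95.4%. The reading holds on average.

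**3. Precision of a limit, one pair per patient.** SE = SD × √(1/n + 2/(n − 1)) = SD × √(0.0100 + 0.0202) = 0.174 SD at n = 100. With t = 1.984 the 95% half-width is 0.34 SD.
- r = 0.9: upper limit exp(2 × 0.170) = 1.40, interval about 1.32 to 1.49
- r = 0.5: upper limit exp(2 × 0.38) = 2.14, interval about 1.88 to 2.44

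Using the exact lognormal SD, √ln(1 + 0.38²) = 0.367, changes little: 1.39 (1.31 to 1.47) and 2.08 (1.84 to 2.36).

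**4. Type I error of the lesion-level t-test.** The documents give neither lesion counts nor an intra-patient correlation (ICC, the between-patient share of the difference variance), so both are assumed. With m lesions in a patient, the variance of the pooled mean is inflated by DE = 1 + (E[m²]/E[m] − 1) × ICC, and the type I error is about 2Φ(−1.96/√DE). Skewed counts are taken as m = 1 + negative binomial with dispersion k, so that Var(m) = (mean − 1) + (mean − 1)²/k.

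| Mean lesions | k | E[m²]/E[m] | DE, ICC 0.2 | Type I | DE, ICC 0.5 | Type I |
|---|---|---|---|---|---|---|
| 3 (all equal) | – | 3.0 | 1.40 | 10% | 2.00 | 17% |
| 3 | 1 | 5.0 | 1.80 | 14% | 3.00 | 26% |
| 3 | 0.3 | 8.1 | 2.42 | 21% | 4.56 | 36% |
| 5 | 1 | 9.0 | 2.60 | 22% | 5.00 | 38% |
| 5 | 0.3 | 16.5 | 4.09 | 33% | 8.73 | 51% |

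Simulation agrees for equal counts of 3: 9.9% at ICC 0.2 and 16.3% at ICC 0.5.

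**5. An interval for a limit that treats lesions as independent.** The plan contains no such interval; this shows what a careless addition would do. Simulated coverage for 100 patients is about 91% (mean 3, k = 1, ICC 0.2), 58–86% across the mean-5 settings, and 93% and 87% for exactly 3 lesions each at ICC 0.2 and 0.5.

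**6. Does pooling bias the limits?** In the mean-5 settings the pooled SD averaged 0.99–1.00 of the true value. The true SE of the upper limit was 0.104, 0.120, 0.147 and 0.184 SD, against 0.174 SD for one pair per patient.

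**The case against.** The strongest reply is that the plan claims little. It says approximately 95%, which is right on average (step 2). It names clustering and offers mixed models. Per-lesion weighting also follows from its chosen target, future lesion differences. All of that stands. It does not supply an interval for any reported quantity, and it leaves the one planned test uncorrected.

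Four stronger readings are tempting and are not supported:
- **That the 95% figure is wrong.** It is not; only its precision is unreported.
- **That a few patients with many lesions drive the limits.** No lesion distribution is given, and uneven counts alone widen sampling error while leaving the pooled SD almost unbiased. A shift needs the further assumption that those patients have a different SD. For example, let 10 patients have 20 lesions each and 90 have 2. If the SD in the 10 is 0.5 or 2 times that of the others, the pooled SD is √(230/380) = 0.78 or √(980/380) = 1.61, against patient-weighted values of 0.96 or 1.14. That is possible, but nothing in the documents shows it.
- **That pooling makes the limits worse than one pair per patient.** In three of the four mean-5 settings the pooled limit is more precise, and in the fourth about equal (step 6). An effective number of patients computed from lesion counts alone ignores the between-patient share and does not describe the precision of the limits.
- **That conclusions should be drawn from the outer confidence bounds.** The plan sets no acceptable limit for such a rule to act on.

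It is also fair that the effect is small with few, evenly spread lesions and low ICC: 93% coverage and 10% type I error with 3 lesions each at ICC 0.2.

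**Conclusion.** The concern holds as a gap in precision and in the planned inference. The missing intervals need no assumption about lesions: at 100 patients with one pair each, a limit is known to about ±0.34 SD, which moves an upper ratio of 1.40 anywhere from 1.32 to 1.49. The clustering part is conditional. With means of 3 to 5 lesions, skewed counts and ICC 0.2 to 0.5, the t-test's error rate is roughly 14–51%, and a lesion-level interval for a limit would cover about 58–91%. These ranges rest on assumed counts and ICC, normal differences and equal SD across patients. The plan's point estimates remain usable; the change is worth making because it is cheap and any judgement of agreement depends on it.

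**What to change.** In Section 11.1.2:
1. Make the random-patient model of the paired differences (transformed if needed) the primary calculation instead of an optional sensitivity analysis. Form the limits as the model mean ± 2 × √(between-patient variance + within-patient variance).
2. Report 95% confidence intervals for the mean difference and for both limits from a bootstrap that resamples patients with all their lesions.
3. Replace the lesion-level paired t-test with the model-based or a patient-clustered test.
4. Report the number of lesions per patient and the two variance components, so that readers can see how much clustering there was.

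The cost is revised wording and a few lines of code, with no extra patients or scans. The reported uncertainty will be wider and look less favourable. The model mean also gives less weight per lesion to patients with many lesions, so the text should say whether the target is a future lesion or a lesion from a future patient.
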